9.3.3.2. Hypoglycemia Events

Hypoglycemic event categories include:

Category	Description
Severe	Assistance required and blood glucose ≤ 70 mg/dL or no value available but responded to glucose treatment
Documented Symptomatic	Blood glucose ≤ 70 mg/dL and typical symptoms of hypoglycemia
Asymptomatic	Blood glucose ≤ 70 mg/dL and no typical symptoms of hypoglycemia
Probable Symptomatic	Typical symptoms of hypoglycemia and no value available but responded to glucose treatment
Relative	Typical symptoms of hypoglycemia and blood glucose > 70 mg/dL

While each event meeting the criteria above will be entered into the hypoglycemia log, only critical (severe) hypoglycemia, documented symptomatic hypoglycemia, asymptomatic hypoglycemia, and probable hypoglycemia will be entered as AEs.

The number and percentage will be summarized by treatment for:

- Each category of hypoglycemic events;
- Any severe or documented hypoglycemic events.

9.3.3.3. Revascularization and Amputations

Revascularization and amputations information are collected in a separate form. Frequency and percentage will be summarized for:

- Type of procedures -cardiovascular related or amputation
- Subjects with any amputation
- Conditions that resulted in amputation
- Location of amputation

Only procedures performed after the first dose of double-blind study drug will be summarized.

9.3.3.4. Renal Failure Events

Frequency and percentage of subjects will be summarized for:

- Any acute kidney event;
- Acute kidney event by stage of disease. If a subject has multiple events, the highest stage will be summarized.

All instances of acute kidney event and their stage will be listed.

9.4. LABORATORY EVALUATIONS

Laboratory tests will include hematology panel, chemistry panel, serum lipids, and urinalysis testing. Hematology, chemistry, and urinalysis will be performed at the following time points: at the screening visit, on baseline visit (week 0), and at weeks 12, 24, and 26. Serum lipids will be performed at the screening visit, on baseline visit (week 0), and on weeks 12, 24, and 26. The study staff will contact each subject prior to a scheduled clinic visit to confirm the time of the visit and to remind the subject of proper fasting practice. A subject must be queried to assess compliance with a minimum of 8-hour fast prior to blood draw to ensure the FPG and triglycerides values can be accurately determined. If a subject has not fasted for approximately 8 hours, the subject must return as soon as can be arranged (within 1 week) to provide a specimen after proper fasting. A list of laboratory tests is included in Table 4.

Low density lipoprotein cholesterol (LDL-C) will be calculated by the Friedewald equation. If triglycerides are > 400 mg/dL, the calculated LDL-C value is invalid by this equation and will be set as missing. Direct LDL-C will be determined in subjects whose triglycerides are > 350 mg/dL at screening visit. All subsequent LDL-C of these subjects will be determined by the same direct LDL-C measurements only. If the triglycerides are >350, a reflex test will be performed based on direct LDL measurement. In that case, two values will be reported but only the direct LDL-C will be used for the analysis as the screening value. The following algorithm will be used to obtain LDL-C values for the analyses:

1. Select subjects (based on the SI unit) who had screening triglycerides >3.4 or >350 based on the conventional unit
2. Take the LDL - direct measurement values only, throughout the study visits for those subjects
3. If screening trig > 350 and no direct LDL-C values have been determined, take the calculated.

Among those subjects who have screening triglycerides >350 and have both calculated and direct LDL-C values, only take the direct LDL-C.

Urinalysis microscopy will be conducted if the subject has a positive result on the leukocyte esterase or nitrite dipstick tests to clarify the significance of the finding. Results of glucose measurement in the urinalysis must be suppressed from the

laboratory reports so the sponsor, investigators, study coordinators, pharmacists, study subjects, and the CEC members will remain blinded to the dosing assignment.

The baseline value will be the latest value obtained on or prior to Day 1. Change from baseline for all continuous parameters will be calculated as the post-baseline value minus the baseline value.

Data summaries will use descriptive statistics (number of subjects [n], mean, standard deviation [SD], median, minimum and maximum) for continuous variables, and frequency and percentage of subjects for categorical and ordinal variables

Observed values (in SI units) and change from baseline over time will be summarized by treatment group. Laboratory data will be classified as low, normal, or high relative to the parameter's reference range. Laboratory abnormalities for each treatment will also be summarized with shift tables for selected parameters.

All laboratory data will be listed. For hematology, chemistry, including serum lipids, columns will be included for normal ranges and individual abnormal laboratory values will be flagged and clinical significance will be indicated. Listing for urinalysis will include the microscopic examination provided for subjects who have a positive result from the urinalysis dipstick evaluation.

Table 4 List of Laboratory Tests

Test Name	Blood or Urine Vol. (mL)	Shipment
Hematology	2 (blood)	Ambient
-Hematocrit (Hct)	-Mean corpuscular volume (MCV)	
-Hemoglobin (Hgb)	-Red cell distribution width (RDW)	
-Mean corpuscular hemoglobin (MCH)	-Red blood cell (RBC) count	
-Mean corpuscular hemoglobin concentration (MCHC)	-White blood cell (WBC) count with differential	
-Platelet count		
Serum Chemistry and Electrolytes	10 (serum)	Ambient
-Albumin (ALB)	-Calcium (Ca)	
-Alanine aminotransferase (ALT)	-Magnesium	
-Aspartate aminotransferase (AST)	-Phosphorus	
-Blood urea nitrogen (BUN)	-Potassium (K)	
-Glucose	-Sodium (Na)	
-Bicarbonate (HCO ₃)	-Total bilirubin	
-Creatinine	-Direct bilirubin	
-Chloride (Cl)	-Uric acid	
-Total protein		
Glycemic Control		Ambient
-Fasting plasma glucose (FPG)	2 (plasma)	
-Hemoglobin A1c (HbA1c)	2 (blood)	
Serum Lipids	6 (serum)	Ambient
-Total cholesterol (TC)	-Low-density lipoprotein cholesterol (LDL-C), calculated	
-High-density lipoprotein cholesterol (HDL-C)	-LDL-C, direct (if applicable)	
-Triglycerides (TG)		
Urinalysis	10 (urine)	Ambient
-Appearance	-Nitrite	
-Bilirubin	-Occult blood	
-Color	-pH	
-Glucose	-Protein	
-Ketones	-Specific gravity	
-Microscopic examination of sediment	-Urobilinogen	
	-Leukocyte esterase	
Urinary Albumin Assessment		Ambient
-UACR	2 (urine)	
Urine pregnancy test (WOCBP)	2 (urine)	Local
Population PK Sampling		Frozen
-Bexagliflozin plasma level	2 (plasma)	

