6.11.1 Sample Collection, Storage, and Shipping

6.11.1.1 Hematology, Blood Chemistry, Serum Lipids, and Glycemic Control Assessments

Blood samples for hematology, chemistry, serum lipids and glycemic control assessments will be collected. Subjects will be in a seated or supine position during blood collection. Samples will be collected at the time points indicated in the schedule of events in [Appendix 1](#) and [Appendix 2](#).

The study staff will contact each subject prior to a scheduled clinic visit to confirm the time of the visit and to remind the subject of proper fasting practice. A subject must be queried to assess compliance with a minimal of 8 h fast prior to blood draw to ensure the FPG and triglycerides values can be accurately determined. If a subject has not fasted for a minimal of 8 h, the subject must return as soon as can be arranged (within 1 week) to provide a specimen after proper fasting.

LDL-C will be calculated by the Friedewald equation. If triglycerides are >400 mg/dL, the calculated LDL-C value is invalid by this equation and will be set as missing. Direct LDL-C will be determined in subjects whose triglycerides are >350 mg/dL at screening visit. All subsequent LDL-C of these subjects will be determined by the same direct LDL-C measurements only.

An investigator can perform additional laboratory testing to diagnose or to follow up an adverse event progression or resolution. Clinical samples should be analyzed in a local laboratory if a fast turnaround time is necessary to determine treatment plan.

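### SAP 9.4 pairs 3.4 in SI units with 350 mg/dL as one triglyceride cut-off; 350 mg/dL is about 3.95 mmol/L, so literal coding could drop usable calculated LDL-C from summaries.

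*SAP*

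**What the plan says.** Protocol 6.11.1.1 and SAP 9.4 state the same measurement rule. LDL-C is calculated by the Friedewald equation, with an upper limit: "If triglycerides are > 400 mg/dL, the calculated LDL-C value is invalid by this equation and will be set as missing". Direct measurement is tied to a screening threshold: "Direct LDL-C will be determined in subjects whose triglycerides are > 350 mg/dL at screening visit". The SAP adds that "If the triglycerides are >350, a reflex test will be performed based on direct LDL measurement".

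SAP 9.4 then gives a three-step algorithm for choosing the LDL-C value to analyse. Step 1 defines a group by its triglycerides at screening: "Select subjects (based on the SI unit) who had screening triglycerides >3.4 or >350 based on the conventional unit". Step 2 fixes which kind of value may be used for everyone in that group: "Take the LDL - direct measurement values only, throughout the study visits for those subjects". Step 3 is a fallback to the Friedewald value, with its own entry condition: "If screening trig > 350 and no direct LDL-C values have been determined, take the calculated".

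A closing sentence says that where screening triglycerides exceed 350 and both kinds of value exist, only the direct one is used. Neither the 3.4 in step 1 nor the 350 in step 3 carries a printed unit. On reporting, the same section says "Observed values (in SI units) and change from baseline over time will be summarized by treatment group".

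**The concern.** Step 1 offers 3.4 and 350 as one threshold in two unit systems. If they differ, the looser one governs, both because the step works on SI values and because it joins the two figures with "or". Subjects between the two thresholds would then be selected into a group limited to direct LDL-C, although neither document plans a direct measurement for them.

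At stake is the completeness of any descriptive LDL-C summary. Values that both documents treat as usable would be left out because of a unit conversion, and the omission would fall on subjects with high triglycerides.

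**Working it through.** **Inputs from the documents**
- SI cut-off in step 1: 3.4, taken as mmol/L (SAP 9.4).
- Conventional cut-off in step 1: 350, taken as mg/dL (SAP 9.4).
- Direct LDL-C planned: screening triglycerides above 350 mg/dL (Protocol 6.11.1.1, SAP 9.4).
- Calculated LDL-C invalid: triglycerides above 400 mg/dL (Protocol 6.11.1.1, SAP 9.4).
- Planned enrolment: 300 subjects (Protocol 9.2).

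**Input assumed**
- The documents give no conversion factor. I use 88.57 mg/dL per mmol/L (mean molar mass about 885.7 g/mol) and test 850 to 900 g/mol, which is 85 to 90 mg/dL per mmol/L.

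**Trying to reproduce 3.4.** Formula: mmol/L = (mg/dL) / factor.
- 350 / 88.57 = 3.95.
- Over the tested range: 350 / 90 = 3.89 and 350 / 85 = 4.12.
- Factor needed for equality: 350 / 3.4 = 102.9, a molar mass of about 1029 g/mol, well outside the range.
- In g/L the figure would be 350 / 100 = 3.5. The cholesterol factor gives 350 / 38.67 = 9.05.
- 300 / 88.57 = 3.39, which rounds to 3.4.

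The printed figure is not reproduced from 350 mg/dL. It matches a 300 mg/dL cut-off, though the documents do not say where it came from.

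**Converting back.** 3.4 x 88.57 = 301 mg/dL (289 to 306 over the tested range).

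**Following the literal steps for a subject screened between about 301 and 350 mg/dL**

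| Rule | Result |
|---|---|
| Step 1, >3.4 SI | Selected |
| Step 2 | Direct LDL-C only, at all visits |
| Measurement rule, >350 mg/dL at screening | No direct value planned |
| Step 3 fallback, read as >350 mg/dL | Does not apply |
| Friedewald limit, >400 mg/dL | Calculated value is valid at any visit with triglycerides at or below 400 |

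The calculated value is therefore not carried into the analysis variable, even at visits where the plan regards it as valid.

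**How many subjects.** The documents give no triglyceride distribution. For illustration, assume log-normal fasting values with median m and log-SD s. The share in the band is Φ(ln(350/m)/s) − Φ(ln(301/m)/s).
- Low end, m = 140, s = 0.45: Φ(2.036) − Φ(1.701) = 0.979 − 0.956 = about 0.024; x 300 = about 7.
- Middle, m = 160, s = 0.50: Φ(1.566) − Φ(1.264) = 0.941 − 0.897 = 0.044; x 300 = about 13.
- High end, m = 180, s = 0.55: Φ(1.209) − Φ(0.935) = 0.887 − 0.825 = about 0.062; x 300 = about 18.

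**The case against.** The strongest reply accepts the mismatch and disputes what follows from it. Four stronger inferences are tempting, and the documents support none of them.

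- **That LDL-C will certainly be lost.** Step 3 prints 350 without a unit. A programmer working in SI, as step 1 directs, needs an SI constant there as well. Reusing 3.4 would make step 3 restore the calculated value for exactly this group. Applying the conventional cut-off in step 1 would also avoid the problem. Every other direct-LDL rule in the section uses 350, so a careful programmer may notice. The loss is conditional on literal coding.
- **That a valid value is lost at every visit.** The band is defined at screening. At a later visit the calculated value is valid only if triglycerides on that day are at or below 400 mg/dL, which the screening value does not guarantee. If the reflex test also runs after screening, an occasional direct value could exist.
- **That the shift tables or the treatment comparison are distorted.** SAP 9.4 limits shift tables to selected parameters and does not name LDL-C among them. The SAP's index of tables titles no serum-lipid table; lipids have a titled listing (16.2.8.4). They may sit within the chemistry summary, but that is not shown. All laboratory data are listed, so no collected value disappears. The selection uses a pre-randomization measurement applied identically in both arms, so it does not by itself bias the comparison. LDL-C is not an efficacy endpoint in SAP section 4 and is not hypothesis-tested.
- **That step 3 contradicts the 400 mg/dL rule.** The set-to-missing rule comes first in the section. Read in order, taking the calculated value for such a subject returns a value already set to missing. The two rules can be read as working together.

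These replies stand and reduce the point to a minor one. They do not make the two cut-offs equal, and a pre-specified algorithm should not depend on a programmer departing from its text.

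**Conclusion.** The SI cut-off in step 1 is wrong as the counterpart of 350 mg/dL: it should be about 3.95 mmol/L, and the printed 3.4 corresponds to about 301 mg/dL. This rests on an assumed conversion factor, but no molar mass in the tested range closes the gap.

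The consequence is less certain than the error. If steps 1 to 3 are coded literally, subjects in the band lose their calculated LDL-C from any descriptive summary. The figure of about 7 to 18 of 300 depends entirely on the assumed distribution and on that literal coding; the true number is unknown. No primary, key secondary or exploratory efficacy result is affected. Severity is minor.

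**What to change.** In SAP 9.4:

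- Step 1: replace >3.4 with >3.95 mmol/L (350 mg/dL), and print both units.
- Step 3 and the closing sentence: state the same threshold, with units, so that one cut-off governs the whole algorithm.
- Optional, as clarification only: say in step 3 that the set-to-missing rule above 400 mg/dL (400 / 88.57 = 4.52 mmol/L) still applies to the calculated value.

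The cost is a few words of SAP text and one programming constant. No new data are needed, and sample collection and laboratory procedures do not change.

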9.5. VITAL SIGNS

Vital signs will be measured at the screening visit, baseline visit (Week 0), and at weeks 6, 12, 24, and 26. Measurements of vital signs will include measurement of supine, sitting and standing blood pressure (BP) measurements, and heart rate. Only the BP measured in the sitting position will be used to determine eligibility. Orthostatic systolic and diastolic BP will be calculated as supine measurement - standing measurement.

For BP, pulse rate, and respiration rate, observed values and change from baseline will be summarized by treatment group and visit using descriptive statistics (n, mean and median, SD, Q1, Q3, minimum, and maximum). BP summary will include supine, sitting, standing and orthostatic BP. Safety analysis set will be used for table summary. Subjects vital sign measurements, including scheduled and unscheduled visits, will be listed.

9.6. ELECTROCARDIOGRAM

A 12-lead electrocardiogram (ECG) will be conducted at the screening visit and at week 24. ECG parameters measured will be the RR interval, PR interval, QRS duration, and QT interval. Each ECG should also be assessed by the investigator for signs of ischemia, clinically significant hypertrophy, and clinically significant T-wave abnormalities or arrhythmia.

For each abnormal ECG result, the investigator shall ascertain if the observation represents a clinically significant change from the screening ECG for that individual subject (this determination, however, does not necessarily need to be made the first time an abnormal result is observed. The investigator may repeat the ECG to verify the results of the original result). If the ECG result is determined to be a clinically significant and abnormal change from baseline for that subject, it is considered an AE.

For the ECG parameters, observed values and change from screening from scheduled visits will be summarized with descriptive statistics (n, mean, SD, median, minimum and maximum) by treatment group and overall at each visit. The maximum change from baseline from scheduled visits will also be provided for ECG parameters.

For the ECG overall assessment, the number and percentage of subjects in each overall assessment category (normal, abnormal but not clinically significant, abnormal and clinically significant, missing) will be presented by treatment group and overall at each visit.

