Bexagliflozin is primarily metabolized to inactive glucuronides by phase II metabolism and is cleared through renal or fecal excretion. Pharmacokinetic (PK) parameters of bexagliflozin and its principal metabolites were determined in patients with T2DM and renal impairment. Reduced clearance due to renal impairment was associated with a 34% or 54% higher systemic exposure in subjects with GFR between 30 and 60 mL/min/1.73 m² or below 30 mL/min/1.73 m², respectively. The half-life was extended from 6.5 h (GRF > 90) to 7.7 h (GFR < 30) with no accumulation of bexagliflozin or its major metabolites. Non-clinical and clinical studies have demonstrated high multiples of safety margins for bexagliflozin tablet, 20 mg. Given the modest increase in drug exposure, dose adjustment in patients with moderate renal impairment is not necessary. A thorough QT study has demonstrated that 100 mg of bexagliflozin administered in an immediate release formulation did not prolong the QT interval or produce adverse changes in any other parameters measured by ECG.

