6.10 Electrocardiography

A 12-lead electrocardiogram (ECG) will be conducted at the time points indicated in the Schedule of Events in [Appendix 1](#) and whenever clinically indicated. This procedure should be performed in the supine position after at least 10 min of rest. ECG parameters measured

will be the RR interval, PR interval, QRS duration, and QT interval. Each ECG should also be assessed by the investigator for signs of ischemia, clinically significant hypertrophy, and clinically significant T-wave abnormalities or arrhythmia.

It is the investigator's responsibility to review the results of the ECG as they become available. For each abnormal ECG result, the investigator shall ascertain if the observation represents a clinically significant change from the screening ECG for that individual subject. This determination does not necessarily need to be made the first time an abnormal result is observed. The investigator may repeat the ECG to verify the original result. If the ECG result is determined to be a clinically significant and abnormal change from baseline for that subject, it is considered to reflect an AE.

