Table 14.3.6.1	Summary of 12-Lead ECG Investigator Overall Assessment by Visit (Safety Analysis Set)
Table 14.3.6.2	Summary of 12-Lead ECG Parameters by Visit: Results and Change from Baseline (Safety Analysis Set)

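### The SAP text summarizes QT without rate correction although RR is recorded on the same ECG; adding QTcF would remove most of the heart-rate confounding at almost no cost

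*SAP*

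**What the plan says.** SAP 4.3 lists the 12-lead ECG among the safety endpoints. On timing, SAP 9.6 says: "A 12-lead electrocardiogram (ECG) will be conducted at the screening visit and at week 24". The recorded parameters are the same four in both documents. SAP 9.6 reads "ECG parameters measured will be the RR interval, PR interval, QRS duration, and QT interval", and Protocol 6.10 says the parameters "will be the RR interval, PR interval, QRS duration, and QT interval".

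The planned analysis is descriptive: "For the ECG parameters, observed values and change from screening from scheduled visits will be summarized with descriptive statistics", namely n, mean, SD, median, minimum and maximum, by treatment group and overall. SAP 9.6 adds: "The maximum change from baseline from scheduled visits will also be provided for ECG parameters". The investigator's reading is also tabulated: "For the ECG overall assessment, the number and percentage of subjects in each overall assessment category". A clinically significant abnormal change is recorded as an adverse event.

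The index of tables has two ECG tables, 14.3.6.1 (overall assessment) and 14.3.6.2 (parameters). Listing 16.2.9.2 gives ECG data by subject. No QTc, correction formula or QTc category appears in the text of either document or in the SAP's indexes.

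Protocol 3.3.2 cites a thorough QT study in which 100 mg, as an immediate-release formulation, "did not prolong the QT interval or produce adverse changes in any other parameters measured by ECG". The same section reports 34% higher systemic exposure at GFR 30 to 60 mL/min/1.73 m².

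**The concern.** QT depends on heart rate. A change in raw QT therefore carries two components: a change in repolarization, which is the safety question, and a change in rate. If rate moves differently in the two arms, a true prolongation can be offset by a faster rate, or a slower rate can look like prolongation.

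A differential rate change is conceivable from the protocol's own description. Section 3.3.3 reports a modest diuretic effect and lower blood pressure with the drug, and section 3.2.5.4 lists hypovolemia and hypotension among the events of special interest. That these would alter heart rate here is inference; the documents do not say so.

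At stake is whether the QT row of a safety table can be read as a repolarization result, and whether individual subjects with a long QTc would be visible. Efficacy, type I error and sample size are not affected.

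**Working it through.** **The plan's own figure.** Neither document gives a numerical ECG target, so there is no ECG figure to reproduce.

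**Inputs.** From the documents: RR and QT are both recorded on each ECG (Protocol 6.10, SAP 9.6), and ECGs are scheduled at screening and week 24 (Protocol Appendix 1, SAP Table 1). Assumed, because the documents give no values: resting rate 70 bpm, QTcF 400 to 440 ms, rate differences of 3 and 5 bpm, and an SD of QT change of 15 to 30 ms.

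**Formulas.** RR = 60/HR (seconds). Fridericia: QTcF = QT/RR^(1/3), so QT = QTcF × RR^(1/3). With QTcF unchanged, the shift in raw QT is QTcF × (RR1^(1/3) − RR0^(1/3)).

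**Shift in raw QT with no true QTc effect, starting from 70 bpm** (RR0 = 0.8571 s, cube root 0.9499):

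| New rate | RR1 (s) | RR1^(1/3) | Shift at QTcF 400 | Shift at QTcF 440 |
|---|---|---|---|---|
| 73 bpm | 0.8219 | 0.9367 | −5.3 ms | −5.8 ms |
| 67 bpm | 0.8955 | 0.9639 | +5.6 ms | +6.1 ms |
| 75 bpm | 0.8000 | 0.9283 | −8.6 ms | −9.5 ms |
| 65 bpm | 0.9231 | 0.9737 | +9.5 ms | +10.5 ms |

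A 3 bpm difference thus moves raw QT by about 5 to 6 ms, and a 5 bpm difference by about 9 to 10 ms.

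**Masking.** A true rise of e ms in QTcF leaves raw QT unchanged when HR1 = HR0 × ((QTcF + e)/QTcF)^3. At 70 bpm and QTcF 400 ms, a 5 ms rise gives 70 × (405/400)^3 = 72.7, so a rate increase of 2.7 bpm hides it. A 10 ms rise gives 70 × (410/400)^3 = 75.4, an increase of 5.4 bpm.

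**Against sampling error.** With the 133 evaluable subjects per arm of SAP 3.7, the 95% half-width for a between-arm mean difference is 1.96 × SD × √(2/133). This is 3.6 ms at SD 15 and 7.2 ms at SD 30. A 3 bpm artefact lies within that range; a 5 bpm artefact exceeds it.

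**Outliers.** The planned minimum and maximum are of raw QT and its change. The longest raw QT may simply belong to the subject with the slowest rate, so these extremes do not identify subjects with a long QTc. The separate RR summary does not repair this, because the correction is nonlinear and must be made within each tracing.

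**The case against.** The strongest opposing case is that this is routine safety monitoring with little riding on it.

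- **The thorough QT study was negative at 100 mg, five times the dose here.** If exposure is proportional to dose and the formulation difference is ignored (both assumptions), 20 mg with 34% higher exposure corresponds to 20 × 1.34 = 26.8 mg, well below 100 mg. This stands and lowers the likely consequence. The study used an immediate-release formulation, whereas Protocol 5.1 describes extended-release tablets, but that alone does not make this trial the key QT evidence.
- **A differential rate change would be seen.** RR is summarized by arm (SAP 9.6), as is pulse rate (SAP 9.5), and the placebo arm cancels rate changes common to both arms. This stands for the arm means. It still leaves no adjusted QT for either the arm or the subject.
- **The plan is not limited to means.** Minimum, maximum, investigator categories, adverse-event capture and a by-subject listing are all planned. A reader might infer that ECG safety as a whole rests on uncorrected QT means; the documents do not support that.
- **The maximum-change statistic is not shown to be redundant.** With one scheduled on-treatment ECG, a reader might infer that it must equal the week 24 change. However, subjects who stop early also have an ECG (Protocol 6.18 and 7.10), and SAP 6.4 maps early-termination visits by study day. Such a subject could contribute to the maximum without a week 24 value, depending on how scheduled visits are read.
- **The shells and SAS code are attachments outside the text provided.** They might contain a QTc derivation. It can be said only that the text specifies none.

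**Conclusion.** The point holds as a minor gap in safety reporting. As written, the plan gives a QT summary confounded with heart rate whenever rate change differs between arms, and it shows no QTc outliers. Under the assumed values, the artefact is about 5 to 6 ms for a 3 bpm difference and about 9 to 10 ms for 5 bpm. These figures show what would follow from such a difference. The documents do not show that one will occur, and nothing in them indicates a QT signal with this drug. The size also rests on Fridericia's formula describing the QT–RR relation adequately. The negative 100 mg study and the RR and pulse-rate summaries make the likely consequence modest. The change is worth making because the required data are already collected.

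**What to change.** In SAP 9.6:

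1. Derive QTcF = QT/(RR in seconds)^(1/3) for each ECG, from the QT and RR of the same tracing.
2. Add QTcF value and change from screening, by arm, to Table 14.3.6.2, and QTcF values to Listing 16.2.9.2.
3. Add counts of subjects by QTcF level and by size of increase. The documents contain no cut-offs, so the sponsor should choose and justify them in the SAP before unblinding.
4. Keep the raw QT summary, since QT is a protocol-named parameter, and keep the maximum-change statistic.

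If the table shells already contain a QTc, a sentence in 9.6 giving the formula would settle the derivation.

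The cost is one derived variable, extra rows in an existing table and an extra listing column. No new ECGs, visits or data collection are needed. Fixing the formula before unblinding also avoids a post hoc choice of correction.
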